#### **5.2.5 DISCHARGE**

Upon discharge, patients will receive a full TRELEGY ELLIPTA inhaler containing 30 doses with instructions to take 1 puff daily in the morning for 30 days. The in-hospital use TRELEGY ELLIPTA used by the patient will be discarded.

The following procedures/assessments will be done prior to hospital discharge:

- Spirometry (FEV1, FVC, FEV1/FVC)
- Peak inspiratory flow rate, measured by the InCheck Dial set at medium resistance.
- Concomitant Medications
- Adverse Events (AE) Assessment
- Patient Satisfaction Questionnaire (St George's Respiratory questionnaire, short version)

In addition, data from the specified assessments will be collected when available, and entered the case report forms (CRFS):

- Vital signs
- Withdrawal from protocol

If for any reason, some of the research assessments at discharge are not performed, the study team may (at investigator's discretion) schedule a follow-up with the subject in the research clinic to obtain the missed assessments.

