### d. Study Endpoints

To attain these objectives, the following study endpoints will be evaluated. Primary and secondary endpoints include the number of in-hospital PRN respiratory therapy treatments, time in between PRN respiratory therapy, change in peak inspiratory flow rate from baseline to discharge, length of stay, at-home drug compliance, 30-day re-admissions (all-cause and respiratory), 30-day survival, cost of respiratory therapy, QOL score, and safety measures (AEs and SAEs; Section 5). See section 8.7 on analytical methods to evaluate these endpoints.

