**b. Eligibility Criteria**

**i. Inclusion Criteria**

- a. Willing and capable of providing written informed consent.
- b. Subjects aged 18 years or older at time of enrollment.
- c. Diagnosis of COPD (per investigator's discretion by prior spirometry results or by spirometry assessment at screening visit) with or without asthma for  $\geq 12$  months.
- d. Hospitalized  $\leq 24$  hours prior to enrollment and currently hospitalized for COPD exacerbation with or without asthma.
- e. Able to properly use the Ellipta medication delivery device.
- f. Able to generate  $\geq 30$  L/min inspiratory flow rate (PIFR) at screening, measured with an InCheck DIAL adjusted to medium low resistance, to document a subject's ability to effectively inhale medication delivered via an Ellipta device.

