**ii. Exclusion Criteria**

- a. Clinically significant lung disease other than COPD with or without asthma.
- b. Positive SARS-CoV-2 test at the time of ED or hospital admission, or any time between admission and enrollment.
- c. History of severe hypersensitivity to milk proteins or demonstrated hypersensitivity to fluticasone furoate, umeclidinium, vilanterol, or any of the excipients.
- d. Unable to perform inspiratory flow or spirometry procedures.
- e. Critically ill patients, or patients with rapidly deteriorating or life-threatening episodes of COPD or asthma including:
  - Patients in critical care unit, or transferred from critical care unit.

- Patients who are transferred to critical care after enrollment will be withdrawn from the study and continue to receive care according to institutional standard practice.
- Patients who initiate Bilevel Positive Airway Pressure (BiPAP) after hospitalization.
  - Patients who use BiPAP at baseline (prior to COPD exacerbation) may be included if BiPAP settings remain consistent with pre-exacerbation settings. Patients will be withdrawn if BiPAP settings are changed after enrollment.

f. Pregnant or lactating women or women of child-bearing potential (WOCBP). Women must meet the non-productive potential definition below to be eligible.

➤ Non-reproductive potential is defined as:

- Pre-menopausal females with one of the following:
  - Documented tubal ligation.
  - Documented hysteroscopic tubal occlusion procedure with follow-up confirmation of bilateral tubal ligation.
  - Hysterectomy.
  - Documented Bilateral Oophorectomy.
- Postmenopausal defined as 12 months of spontaneous amenorrhea with an appropriate clinical profile (e.g., age appropriate, >45 years, in the absence of hormone replacement therapy). In questionable cases for women <60 years of age, a blood sample with simultaneous follicle stimulating hormone and estradiol falling into the central laboratory's postmenopausal reference range is confirmatory. Females under 60 years of age, who are on HRT and whose menopausal status is in doubt, are required to use a highly effective method to avoid pregnancy if they wish to continue their HRT during the study. Otherwise, they must discontinue HRT to allow confirmation of postmenopausal status prior to study enrolment. For most forms of HRT, at

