### **8.2. Measurement of Efficacy**

Efficacy will be assessed by the number of in-hospital PRN respiratory therapy treatments with PRN nebulized albuterol 2.5mg, time in between PRN respiratory therapy, change in respiratory inspiratory flow rate measured by InCheck DIAL at medium resistance from baseline to discharge, length of stay, at-home drug compliance, 30-day re-admissions (all-cause and COPD exacerbation), 30-day survival, cost of in-hospital respiratory therapy, and response to a patient satisfaction questionnaire (QOL questionnaire).

Drug compliance at home will be assessed through follow-up phone call at 30-day post-discharge. Compliance will be calculated as the difference between 100 and the percentage of doses left on the TRELEGY ELLIPTA inhaler out of 30.

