## **8.7. Statistical Considerations**

### **a. Study Design Endpoints**

Primary and secondary endpoints include the number of in-hospital PRN respiratory therapy treatments, time in between PRN respiratory therapy, change in peak inspiratory flow rate measured with an InCheck DIAL through medium low resistance from baseline to discharge, length of stay, at-home drug compliance, 30-day re-admissions (all-cause and respiratory), 30-day survival, cost of respiratory therapy, and QOL score.

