### **c. Analysis of Primary Endpoint**

The number of PRN respiratory treatments during hospitalization will be reported as the median [quartile 1, quartile 3] and as the average number of PRN respiratory treatments per inpatient day  $\pm$  standard deviation. A comparison between patients who were and were not readmitted within 30-days will be made using a Wilcoxon signed rank test for the number of PRN respiratory treatments. Additionally, the incident rate ratio of the average per-inpatient

day PRN treatments will be estimated using a robust Poisson regression model comparing patients who were readmitted within 30-days to those who were not.

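### The 8.7.c rate ratio of PRN treatments by 30-day readmission is unadjusted although screening FEV1 is collected; a prespecified adjusted ratio should stand beside it

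*Combined protocol and SAP*

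**What the plan says.** **Collection.** Section 5.2.2 lists spirometry as a screening procedure without restriction. Section 5.2.5 repeats it before discharge: "Spirometry (FEV1, FVC, FEV1/FVC"). If discharge assessments are missed, the investigator may arrange a research-clinic visit to obtain them.

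**Eligibility.** Exclusion criterion d reads "Unable to perform inspiratory flow or spirometry procedures". Inclusion criterion c gives spirometry a diagnostic role: "Diagnosis of COPD (per investigator's discretion by prior spirometry results or by spirometry assessment at screening visit").

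**Endpoints.** The only lung measurement in the endpoint lists is inspiratory flow. Section 2.d has "change in peak inspiratory flow rate from baseline to discharge, length of stay, at-home drug compliance", section 8.2 has "change in respiratory inspiratory flow rate measured by InCheck DIAL at medium resistance from baseline to discharge", and section 8.7.a has "change in peak inspiratory flow rate measured with an InCheck DIAL through medium low resistance from baseline to discharge". The efficacy assessments in the Synopsis follow the same pattern. FEV1, FVC and their ratio appear in none of the four.

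**Analysis.** The effect measure in section 8.7.c is "the incident rate ratio of the average per-inpatient" (the sentence runs over a page break). It comes from a robust Poisson model that contrasts readmitted with other patients. No covariate is named. Section 8.7.d, which covers the secondary comparisons by readmission and the historical comparison, names none either.

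**The concern.** The rate ratio is the only effect estimate in the primary-endpoint section. Patients with worse lung function on admission could plausibly need more PRN treatment and also return to hospital more often. If so, a ratio above 1 would appear even when PRN need says nothing about readmission beyond how ill the patient was at entry. The trial plans to measure a standard marker of that severity before the in-hospital PRN treatments are counted, but the plan does not bring it into the model.

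At stake is what a reader can take from the ratio. As planned, it can show that PRN use differs by later readmission. It cannot show whether the difference goes beyond measured baseline lung function. If adjustment is not prespecified, the decision whether to adjust could also be made after the data are seen.

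**Working it through.** **The plan's own figures.** Section 4.a: 120 × 2/3 = 80 enrolled, which reproduces the stated 80. With 30-day follow-up in 80%, 80 × 0.80 = 64 patients. The documents state no power, alpha or effect size, and nothing that links FEV1 to PRN use or readmission. Every effect below is therefore an assumption.

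**Approximate size.** Let S be a severity score with SD 1 (worse screening lung function is higher). Assume S acts on readmission and on the PRN rate, with no direct link between those two. The difference in mean S between readmitted and other patients is then about ln(OR), where OR is the readmission odds ratio per SD. If the PRN rate is multiplied by r per SD, the apparent rate ratio is about r^ln(OR).

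- Lower end, OR 1.5 and r 1.25: ln(1.5) = 0.405, and 1.25^0.405 = 1.09 (log scale 0.09).
- Upper end, OR 2 and r 1.40: ln(2) = 0.693, and 1.40^0.693 = 1.26 (log scale 0.23).

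**Check by simulation.** Readmission was logistic in S with 20% readmitted (assumed). The PRN rate was log-linear in S. Large-sample unadjusted ratios with no direct link were:

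| PRN rate multiplier per SD | OR 1.25 | OR 1.5 | OR 2 |
|---|---|---|---|
| exp(0) = 1 | 1.00 | 1.00 | 1.00 |
| exp(0.2) | 1.04 | 1.08 | 1.14 |
| exp(0.3) | 1.07 | 1.13 | 1.21 |
| exp(0.5) | 1.12 | 1.22 | 1.38 |

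With OR 1 the ratio is also 1.00 throughout, so severity must act on both PRN use and readmission to move it. The approximation agrees: for exp(0.3) and OR 1.5 it gives exp(0.3 × 0.405) = 1.13.

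**At the trial's size.** Samples of 64 were simulated with a mean stay of 4 days, 2 PRN treatments per day at average severity, and gamma variation between patients (shape 2), all assumed. At 20%, about 0.20 × 64 = 13 patients are readmitted.

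| PRN multiplier, OR | Mean ratio, unadjusted | Mean ratio, adjusted for S | SD of log ratio, unadjusted / adjusted |
|---|---|---|---|
| 1, 1 | 0.98 | 0.98 | 0.28 / 0.28 |
| exp(0.2), 1.5 | 1.07 | 0.99 | 0.30 / 0.29 |
| exp(0.3), 1.5 | 1.10 | 0.99 | 0.30 / 0.28 |
| exp(0.3), 2 | 1.19 | 0.99 | 0.30 / 0.30 |
| exp(0.5), 2 | 1.29 | 0.96 | 0.34 / 0.30 |

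Adjustment removes the severity component and leaves precision about the same. The shift of 0.09 to 0.23 on the log scale is less than one standard error (0.28 to 0.34). These runs adjust for S itself; real FEV1 would capture only part of severity and so remove only part of the shift.

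**The case against.** The strongest reply is that confounding presupposes a question the plan does not ask. The primary objective (2.a) is to establish PRN requirements, and no secondary objective in 2.b seeks a severity-independent link between PRN use and readmission. Section 8.7.c contrasts PRN use between groups defined by a later event, and an unadjusted contrast is a valid descriptive result. This stands: a reader might infer that the ratio is confounded as a matter of fact, and the documents do not support that. They do not, however, label the ratio as descriptive.

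A second reply is that the assumed bias is smaller than the study's sampling error. This also stands. It limits the importance of the point, but a systematic shift is not removed by being smaller than the standard error, and adjusting cost no precision in the runs above.

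Three further inferences are tempting and should not be drawn:

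- *That spirometry serves no purpose.* Criterion c gives the screening test a diagnostic role, and the general reporting rule at the start of section 9 (statistical analysis) could cover a descriptive summary.
- *That the discharge measurement should enter the model.* It follows the in-hospital PRN treatments and is not a baseline value.
- *That change in FEV1 ought to be an endpoint.* No objective concerns spirometric recovery. Sections 5.1 and 5.2.4 also place patients on systemic corticosteroids, so in a single-arm study a change could not be attributed to the study inhaler.

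Finally, the number readmitted limits the precision of the contrast. It does not act as an events-per-variable cap here, because PRN use is the outcome and readmission the grouping variable.

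**Conclusion.** The point holds as an improvement to the analysis, not as a demonstrated bias. The documents establish that screening spirometry is planned for every patient, that no endpoint or model uses it, and that the 8.7.c ratio is unadjusted. A ratio above 1 may therefore partly reflect baseline severity. How much is unknown: about 1.09 to 1.26 under the stated assumptions, and 1.00 if severity does not affect both PRN use and readmission. With about 64 followed patients this lies within one standard error, itself computed under an assumed 20% readmission rate and assumed PRN use. The change is worth making because the covariate is already collected and the adjusted estimate addresses a question the unadjusted one cannot.

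**What to change.** In section 8.7.c:

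1. Keep the unadjusted rate ratio and call it a descriptive association.
2. Prespecify a second robust Poisson rate ratio with screening FEV1 as a covariate, stating the scale on which FEV1 enters, and report it beside the first with a 95% confidence interval.
3. State that only the screening value is used. Since 8.7.e rules out imputation, also give the unadjusted ratio in the patients with screening FEV1, so that the two estimates compare the same people.

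A descriptive summary of FEV1 change from screening to discharge is optional. If given, it should flag values obtained at a later clinic visit and claim no effect of the inhaler.

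**Cost.** No new data are needed. There is one more estimate to report, and because section 8.7 is protocol text, section 16.1 requires a written amendment. Adjustment removes only the severity that FEV1 captures, and the interval will not become narrower.

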## 1. SYNOPSIS

Summary/Rational:	This phase IV, post market approval single-center, open-label study will be used evaluate to a more standardized open-label protocol which would allow for a more accurate assessment of intervention outcomes when a combination LABA/LAMA/ICS inhaler is used as the primary scheduled daily inhaled therapy.
Study Objectives:	
Primary objective:
 

1. To establish the requirements for PRN respiratory therapy treatments in patients hospitalized with the diagnosis of COPD exacerbation receiving once-daily ICS/LABA/LAMA (fluticasone furoate/umeclidinium/vilanterol) therapy.

 
Secondary objectives:
 

1. To measure the distribution of inspiratory flow rates with an InCheck Dial device set on measuring PIF using the medium low resistance setting in patients admitted with COPD exacerbations at Baylor University Medical Center, Dallas TX at the time of enrollment and day of discharge

2. To determine the hospital length of stay for patients admitted with the diagnosis of COPD exacerbation

3. To monitor and report any side effects from using once-daily ICS/LABA/LAMA or PRN therapy.

4. To evaluate the transition of care in delivering respiratory therapy medications from hospital to home

5. To compare the number of PRN treatments, length of hospital stay, and rate of readmissions with findings in a previously

	
analyzed historical cohort of 60 patients in our healthcare system.
 
Exploratory Objectives
 
To determine the cost of respiratory care for patients hospitalized with the diagnosis of COPD exacerbation.

Study Design:	Phase IV, post market approval, single-center, open-label study
Number of Subjects:	Up to 120 subjects will be enrolled out of which approximately 80 will be TRELEGY ELLIPTA Treated Subjects; this allows for an anticipated acceptance rate of 2/3

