  - Documented tubal ligation.
  - Documented hysteroscopic tubal occlusion procedure with follow-up confirmation of bilateral tubal ligation.
  - Hysterectomy.
  - Documented Bilateral Oophorectomy.
- Postmenopausal defined as 12 months of spontaneous amenorrhea with an appropriate clinical profile (e.g., age appropriate, >45 years, in the absence of hormone replacement therapy). In questionable cases for women <60 years of age, a blood sample with simultaneous follicle stimulating hormone and estradiol falling into the central laboratory's postmenopausal reference range is confirmatory. Females under 60 years of age, who are on HRT and whose menopausal status is in doubt, are required to use a highly effective method to avoid pregnancy if they wish to continue their HRT during the study. Otherwise, they must discontinue HRT to allow confirmation of postmenopausal status prior to study enrolment. For most forms of HRT, at least 2 to 4 weeks will elapse between the cessation of therapy and the blood draw; this interval depends on the type and dosage of HRT. Following confirmation of their post-menopausal status, subjects can resume use of HRT during

	the study without use of a highly effective method to avoid pregnancy.
Sponsor:	GlaxoSmithKline plc. (GSK)-Only provide the drug.  Baylor Scott and White Research Institute (BSWRI)
Principal Investigators:	[name]
Primary Study Site/Data Center:	Annette C. & Harold C. Simmons Transplant Institute  [name]  [contact]  [contact]
Medication:	TRELEGY ELLIPTA (fluticasone furoate 100 mcg, umeclidinium 62.5 mcg, and vilanterol 25 mcg inhalation powder)
Medication Delivery Device:	ELLIPTA

Efficacy Assessments:	

➤ Number of in-hospital PRN respiratory therapy treatments with PRN nebulized albuterol 2.5mg.

➤ Time in between PRN respiratory therapy.

➤ Change in respiratory inspiratory flow rate measured by InCheck DIAL at medium resistance from baseline to discharge.

➤ Length of stay.

➤ At-home drug compliance.

➤ 30-day re-admissions (all-cause and COPD exacerbation), 30-day survival, cost of in-hospital respiratory therapy, response to a patient satisfaction questionnaire (QOL questionnaire).

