### b. Secondary Objectives

1. To measure the distribution of inspiratory flow rates with an InCheck Dial device set on measuring PIF using the medium low resistance setting in patients admitted with COPD exacerbations at Baylor University Medical Center, Dallas TX at the time of enrollment and day of discharge.
2. To determine the hospital length of stay for patients admitted with the diagnosis of COPD exacerbation.
3. To monitor and report any side effects from using once-daily ICS/LABA/LAMA or PRN therapy.
4. To evaluate the transition of care in delivering respiratory therapy medications from hospital to home.
5. To compare the number of PRN treatments, length of hospital stay, and rate of readmissions with findings in a previously analyzed historical cohort of 60 patients in our healthcare system.

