#### Assessments and procedures at screening

- Informed consent
- Assignment of screening number
- Inspiratory Flow Rate (PIFR) evaluation, with InCheck DIAL device set to measure medium low resistance. The best of 3 maximum inspiratory flow measurements, taken from RV will be recorded.
- Spirometry (FEV1, FVC, FEV1/FVC)
- Inclusion/Exclusion Criteria
- Demographics
- Medical History
- Decision by investigator to enroll subject or to declare screen failure.

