#### **5.2.3 ENROLLMENT (within 24 hours of admission)**

The following procedures/assessments will be done the morning or following morning of admission into study:

- Concomitant Medications
- Adverse Events (AE) Assessment
- Patient Satisfaction Questionnaire (St George's Respiratory questionnaire-short version)

In addition, data from the specified assessments will be collected when available, and entered the case report forms (CRFs):

- Vital signs

- Physical Exam

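### Inspiratory flow is set at medium low resistance at screening but at medium resistance at discharge, so the change endpoint mixes two settings if the visit instructions are followed as written

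*Combined protocol and SAP*

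**What the plan says.** Inspiratory flow is scheduled twice. At screening (section 5.2.2) it is measured "with InCheck DIAL device set to measure medium low resistance", taking the best of three efforts. At discharge (section 5.2.5) the list reads "Peak inspiratory flow rate, measured by the InCheck Dial set at medium resistance". The enrollment list in section 5.2.3, introduced by "The following procedures/assessments will be done the morning or following morning of admission into study", contains no flow measurement, and neither does the treatment list in section 5.2.4.

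The change endpoint is defined with a setting in three places, and they disagree:

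- Synopsis, Efficacy Assessments: "Change in respiratory inspiratory flow rate measured by InCheck DIAL at medium resistance from baseline to discharge"
- Section 8.2: "change in respiratory inspiratory flow rate measured by InCheck DIAL at medium resistance from baseline to discharge"
- Section 8.7.a: "change in peak inspiratory flow rate measured with an InCheck DIAL through medium low resistance from baseline to discharge"

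Secondary objective 1, in the synopsis and again in section 2.b, is "To measure the distribution of inspiratory flow rates with an InCheck Dial device set on measuring PIF using the medium low resistance setting", and it applies "at the time of enrollment and day of discharge". Both versions of the flow eligibility criterion (synopsis and section 4.b.i) also specify medium low. Section 2.d and the secondary analysis in section 8.7.d name the change endpoint without a setting.

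**The concern.** A change score is interpretable only if both readings are taken under the same conditions. Here the two visit instructions, which are what staff carry out, name different resistance settings. If flow through the two settings differs, the reported change is the patient's change plus a setting effect. With one arm and no second matched reading, the two cannot be separated.

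Two results are exposed: the within-patient change in inspiratory flow, which is a named endpoint, and the distribution of flow at discharge, which is half of secondary objective 1. The documents do not show whether the setting is recorded with each reading. If it is not, mixed pairs could not be identified afterwards. The primary endpoint, the count of PRN treatments, is not touched.

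**Working it through.** The plan gives no figure to reproduce, so the check sets every statement side by side and then traces which readings feed the endpoint.

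| Place | Governs | Baseline setting | Discharge setting |
|---|---|---|---|
| Synopsis, secondary objective 1 | flow distribution | medium low | medium low |
| Section 2.b, objective 1 | flow distribution | medium low | medium low |
| Synopsis, inclusion criterion 6 | eligibility at screening | medium low | – |
| Section 4.b.i, criterion f | eligibility at screening | medium low | – |
| Section 5.2.2 | screening instruction | medium low | – |
| Section 8.7.a | change endpoint | medium low | medium low |
| Synopsis, Efficacy Assessments | change endpoint | medium | medium |
| Section 8.2 | change endpoint | medium | medium |
| Section 5.2.5 | discharge instruction | – | medium |
| Sections 2.d and 8.7.d | change endpoint | not stated | not stated |

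**Counts.** Overall, six places say medium low and three say medium. By time point, the baseline reading is medium low in six and medium in two; the discharge reading is medium low in three and medium in three.

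**Trace.** The only scheduled baseline is the screening reading (medium low). The only scheduled discharge value is the one in section 5.2.5 (medium). Following both literally gives medium at discharge minus medium low at baseline. That matches neither section 8.7.a nor the pair formed by the synopsis efficacy list and section 8.2, and it departs from objective 1 at discharge.

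**Effect on the change score.** Let D be the discharge flow at medium low and r the ratio of medium to medium-low flow. Then

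observed change = true change − D × (1 − r).

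The documents give neither r nor its direction, and no distribution of flow. The only flow figure is the 30 L/min eligibility floor, which applies at screening; no floor is stated for discharge. Using 30 L/min for D only to show scale:

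- each 1% difference between settings: 30 × 0.01 = 0.3 L/min
- assumed difference of 0%: 30 × 0 = 0 L/min
- assumed difference of 20%: 30 × 0.20 = 6 L/min

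The shift is proportionally larger at higher flows. The 0 to 20% range is an assumption.

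**Effect on the planned comparison.** Section 8.7.d compares the change between readmitted and non-readmitted patients. How far the setting effect cancels depends on its form:

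- a constant offset k in every pair: k − k = 0, so it cancels exactly;
- an offset proportional to flow: the remainder is (1 − r) × (difference between groups in mean discharge flow), which is zero only if those means are equal;
- a constant offset k in only some pairs: the remainder is k × (difference between groups in the share of mixed pairs).

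The descriptive summary of change has no such protection under any of the three.

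**The case against.** The best counter-argument is that *medium* is loose wording for *medium low*. Section 2.d refers the reader to section 8.7 for the analysis of the endpoints, and section 8.7.a specifies medium low from baseline to discharge, as does objective 1. Every endpoint definition that names a setting uses the same one at both visits, so a mixed score arises only by combining the two visit instructions. The count of six to three also overstates the case, because three of the six concern screening only; for the discharge reading the split is three to three. Finally, the numerical range has no source in the documents, and the endpoint is secondary.

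Most of this is fair. The cross-reference makes medium low the likelier intention, the like-for-like split is even, and the range demonstrates no bias. None of it corrects the instruction in section 5.2.5, which is what staff follow on the day. No text equates the two terms, the amendment history does not address them, and the shorter term appears in three separate places. If it is a slip, it costs little to correct. If it is not, the change endpoint is confounded with the setting.

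**Conclusion.** The contradiction is certain, and it reaches the operational instructions. As written, sections 5.2.2 and 5.2.5 produce a change score from two settings that no definition in the plan supports. This should be fixed, on the strength of the conflict between those two instructions rather than of the numerical illustration.

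The size of any bias cannot be calculated. The illustrative 0 to 6 L/min rests on an assumed 0 to 20% difference at 30 L/min and includes zero. The documents cannot show whether mixed pairs were actually taken. The consequence is confined to the change in inspiratory flow and the discharge flow distribution. The readmission comparison is affected only if the offset varies with flow or between patients.

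**What to change.** Replace medium with medium low in the synopsis Efficacy Assessments, section 5.2.5 and section 8.2. That direction fits the only scheduled baseline, objective 1 and section 8.7.a; choosing medium instead would require an added baseline reading. Record the setting with each flow reading if this is not already done. Repeating the best-of-three rule in section 5.2.5 would be a useful optional addition.

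If discharge readings have already been taken, keep them all. Report the change and the discharge distribution separately by setting, with matched pairs as the main result, mixed pairs flagged and counted, and pairs of unknown setting counted. If there are no matched pairs, present the mixed-pair change as descriptive only and state that it cannot be separated from the setting.

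The cost is three wording edits and one data field. The matched-setting analysis will have fewer patients. Among those already discharged the number could be zero if section 5.2.5 was followed literally, and section 8.7.e allows no imputation to replace those values.
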